5.3 Study Schedule

Figure 1. Study schedule with overview of procedures and evaluations

5.4 Recruitment

5.4.1 Sensitisation

General sensitisation will be conducted at the four study sites, surrounding antenatal clinics, and major referral centres, aiming to raise awareness of both KMC and the planned study. This will begin prior to the internal pilot and continue throughout the duration of the study.

Following identification of an eligible participant, initial sensitisation of the parent/caregiver will be done by telling them about the study and inviting them to participate.

5.4.2 Informed consent

Written informed consent will be sought from the parents of all participants for the following neonatal participation: inclusion in the study; collection of sociodemographic data; collection of clinical data; and randomisation to study arm. Consent will also be taken for the possibility that the parent/caregiver will provide continuous skin-to-skin contact, if randomised to that arm. Additionally, consent will be taken for the collection of household socioeconomic and cost data, as well as data on infant-caregiver attachment and women's well-being.

Medical officers or study nurses will obtain informed consent. The preferred person to provide informed consent for neonatal involvement is the mother. If a mother is unavailable or too ill to provide consent, informed consent will be obtained from the father. Once the mother is available and feeling well enough, the informed consent process will be repeated to confirm her consent for her baby's continued participation in the study.

Impartial and literate witness will be used during consent for illiterate parents, as per ICH-GCP guidance.

Further details regarding the informed consent process are detailed in section 14.5.

5.4.3 Enrolment

Following informed consent, a unique study identification number will be allocated, and the neonatal enrolment log will be completed. A separate maternal/caregiver enrolment number will be allocated, and a maternal/caregiver enrolment log sheet completed to identify and link the unique study ID numbers of parent/caregiver and neonate. This will include options for entering multiple caregivers, in the event of the mother not being available immediately and other family members providing the intervention.

5.5 Collection of Baseline Data

5.5.1 Clinical data

Study staff will collect the following clinical data as soon as possible after enrolment, with the exception of gestational age assessment and length measurement, which may be delayed to within 48h of admission. If any medical therapies (e.g., oxygen) have already been started by study staff, these will be continued throughout the clinical data collection process.

Research staff will be trained in appropriate infection control procedures and study specific protocols will detail infection control measures for the use of study equipment (pulse oximeters, weighing scales, etc.) to avoid cross-infection and contamination between participants.

- Axillary temperature will be measured with a digital thermometer (in degrees Celsius). Three measurements will be taken to enable calculation of the mean value.
- A capillary sample for blood glucose measurement will be obtained by heel prick using appropriately sized lancets and study-specific blood glucose machines at each site.
- Physical examination will be conducted.
- Head circumference [occipitofrontal circumference (OFC)] will be measured. • Gestational age will be estimated using the Ballard score (Appendix C)
- Crown-foot length will be measured.

The collection of baseline clinical data is estimated to take approximately 30 minutes, not including gestational age and length measurement. Data will be recorded in the eCRF (Appendix D) by trained study staff.

5.5.2 *Sociodemographic data*

Following the collection of baseline clinical data (with exception of gestational age and length measurement), trained study staff will collect the following sociodemographic data using standardised parent interviews and medical records (antenatal and hospital). Data will be recorded in the eCRF by trained study staff.

- Maternal details: contact details; date of birth; marital status; employment; highest level of education; date of last menstrual period (LMP); significant medical history; antenatal history (gravidity, parity, complications, interventions)
- Perinatal details: mode of delivery; presence of sepsis risk factors; administration of antenatal steroids and antibiotics in preceding 7d; APGAR scores; date and time of birth
- Neonatal details: gender; age at admission; admission diagnoses; multiple birth; interventions since birth (resuscitation, medications, other therapies)
- SARS-CoV-2 signs/symptoms and testing status/results for mothers and babies recruited after 25 March 2020

5.5.3 *Socioeconomic Data*

Trained study staff will collect the following socioeconomic data within 48h of admission, using standardised parent interviews. Data will be recorded in eCRF by trained study staff.

- Women's Capability Index: questionnaire to be administered to mothers immediately following collection of the above maternal sociodemographic data
- Household details: household density; number of children; occupation and highest educational level of other household members; data to be obtained as soon as is practical (may be collected after randomisation/allocation in order to avoid delays in starting intervention)

Trained study staff will also inform families that, over the coming month, they will be asked about their expenditures and the activities of members of their household (and any extended family members who become involved in care provision) in order to evaluate the economic impact of KMC relative to standard care. Data that will be collected includes the following:

- Expenditures: Medical supplies/hospital fees; food; transport
- Activities: Extent to which members of their household (and any extended family who become involved in care provision) were able to participate in their usual activities (paid work, household work, farming own land, or school/play) versus took time to care for/support the baby and/or parents, and any income/revenue lost as a result of this.

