Defined as $\text{SpO}_2 < 88\%$ in oxygen AND ≥ 1 of:

- Respiratory rate < 20 or > 100 breaths/min
- Apnoea requiring bag-mask ventilation
- HR < 100 or > 200 bpm

Major congenital malformation:

A malformation that is present at birth and which is incompatible with life or requires immediate surgical management

Severe jaundice:

Jaundice occurring within the first 24h after delivery and/or visible in sclera, palms or soles

PRIMARY OUTCOME

Early neonatal mortality:	Death of a neonate within the first 7 days after birth (day 0-6)
----------------------------------	--

SECONDARY OUTCOMES

Hypothermia:	Axillary temperature below the normal range (36.5°C – 37.5°C); can be subcategorised as follows: Mild: 36.0°C – 36.4°C Moderate: 32.0°C – 35.9°C Severe: <32°C
---------------------	---

Duration of hospital admission:	Mean time (days and hours) from hospital admission to discharge
--	---

Breastmilk feeding:	Process of feeding a mother's breastmilk to her infant, either directly from the breast or by expressing milk from the breast and feeding it to the infant by nasogastric tube, bottle, cup, or spoon, to provide calories, macronutrients, and micronutrients (10)
----------------------------	---

Time from intervention/control procedures starting to exclusive breastmilk feeding:	Mean time (days and hours) from initiation of intervention/control procedures to exclusive breast milk feeding
--	--

Neonatal mortality:	Death of a neonate within the first 28 days of life
----------------------------	---

Time from intervention/control procedures starting to clinical stabilisation:	Mean time (days and hours) from initiation of intervention/control procedures to clinical stabilisation, with stability defined as having met the following criteria for a continuous period of at least 24h: (i) Breathing spontaneously with SpO ₂ >90% in room air (ii) No need for supplemental oxygen or CPAP (iii) Respiratory rate 40 to <60 breaths per minute (iv) No apnoea (v) Heart rate 80 to <180 beats per minute (vi) Axillary temperature 36.0 to 37.4 degrees Celsius (vii) No need for IV fluids
--	---

Time from intervention/control procedures starting to death:	Mean time (days and hours) from initiation of intervention/control procedures to death
---	--

Frequency of readmission:	Mean frequency of episodes in which an infant who had been discharged from a hospital is admitted again during a defined time period

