1.4.2 Secondary outcomes

- Prevalence of hypothermia at 24 hours post-randomisation
- Mean duration of hospital admission (days and hours)
- Mean time from intervention/control procedures starting to exclusive breastmilk feeding (days and hours)
- Mortality within 28 days
- Time from intervention/control procedures starting to clinical stabilisation (days and hours)
- Time from intervention/control procedures starting to death (days and hours)
- Frequency of readmission
- Mean daily weight gain (g/day) at 28 days
- Infant-caregiver attachment at 28 days
- Women's well-being at 28 days

2. Background

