5.6 Randomisation

Randomisation will take place following collection of necessary baseline data and before the intervention or control procedures start. The details of the randomisation method are outlined in section 3.2.1. In situations where both twins are eligible for enrollment, they will be allocated to the same arm.

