10.2.2 Primary and secondary outcome analyses

The primary and secondary outcome analyses will be carried out on all neonates as randomised ('intention to treat'). Analysis will follow a pre-specified analysis plan approved by the TSC and DSMB prior to unblinding the study database. The criterion for statistical significance at the final analysis will be $P < 0.05$. The rate of loss to follow up will be reported. We will report risk ratios for mortality seven days after enrolment (primary outcome) and 28 days after enrolment (secondary outcome) for intervention versus control with associated 95% confidence intervals. Secondary outcomes: time from intervention/control procedures starting to death and length of hospital stay, will be analysed using Kaplan-Meier plots and the hazard ratios with accompanying 95% CI calculated using Cox proportional hazards regression. All other secondary outcomes will be analysed using appropriate regression models accounting for the nature of the distribution of the outcome and results will be presented as appropriate effect sizes with a measure of precision (95% confidence intervals). Both unadjusted analyses and analyses adjusted for stratification factors will be carried out. Additional exploratory analyses will control for any baseline measures that appear to be imbalanced between arms.

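### The stated analyses of hypothermia at 24 hours admit baseline axillary temperature only through an exploratory, imbalance-triggered adjustment; naming it in advance costs almost nothing, for a gain between nil and modest

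*Protocol*

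**What the plan says.** - **Outcome.** Section 1.4.2 of the Protocol lists "Prevalence of hypothermia at 24 hours post-randomisation". The Definitions give hypothermia as "Axillary temperature below the normal range (36.5°C – 37.5°C"), so the outcome is a dichotomised axillary temperature.
- **Baseline measurement.** Section 5.5.1 has axillary temperature taken by digital thermometer after enrolment: "Three measurements will be taken to enable calculation of the mean value". The baseline clinical items are due promptly, "with the exception of gestational age assessment and length measurement, which may be delayed to within 48h of admission". Temperature is not among the exceptions.
- **Timing.** Section 5.6: "Randomisation will take place following collection of necessary baseline data and before the intervention or control procedures start".
- **Analysis.** Section 10.2.2: "Both unadjusted analyses and analyses adjusted for stratification factors will be carried out". The stratification factors are birthweight band and recruitment site (Section 3.2.1). The next sentence sets the route for anything else: "Additional exploratory analyses will control for any baseline measures that appear to be imbalanced between arms". The regression model for hypothermia is not named, and the section refers to a separate pre-specified analysis plan.

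**The concern.** The trial collects the baseline value of the variable that defines this outcome, yet the protocol's non-exploratory analyses leave it out. The one route in is triggered by apparent imbalance. No threshold is given, so the choice of covariate depends on the observed data. The trigger is also the wrong criterion: precision from adjustment comes from how well the covariate predicts the outcome, not from how far it differs between arms. A baseline temperature that is strongly prognostic but balanced would be excluded; one that is weakly prognostic but imbalanced by chance would be included.

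At stake is some precision on a secondary outcome tied to thermal control, which Section 2.1 names among the main causal pathways. Validity is not at stake: leaving out a prognostic covariate does not bias a randomised comparison.

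**Working it through.** **1. The plan's own figures.** The protocol gives no prevalence, effect, power or precision for hypothermia. Its only sample-size calculation is for mortality (Section 10.1): 25% v 19.4%, 80% power, 5% significance (taken as two-sided), 875 per arm. With the pooled-variance formula:

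n = [1.960·√(2·0.222·0.778) + 0.842·√(0.25·0.75 + 0.194·0.806)]² / 0.056² = 864 per arm (899 with continuity correction).

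Power at 875 per arm is 80.5%, and 1750/0.80 = 2188. The plan's figures reproduce. They do not bear on hypothermia; 1750 serves below only as an illustrative number of babies.

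**2. Was temperature measured before randomisation?** Three texts bear on this.
- Section 5.5.1 exempts only gestational age and length from prompt collection.
- Section 5.5.3 says expressly that household details may follow randomisation; temperature carries no such permission.
- Section 5.6 puts randomisation after the necessary baseline data but does not itemise them.

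Before randomisation is the natural reading, though not an explicit statement.

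**3. Size of the gain, on assumptions.** Assumed: baseline and 24-hour temperature are bivariate normal with correlation r, and hypothermia is the lower tail with prevalence p. Neither r nor p is in the protocol. For a standardised baseline value x:

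- m(x) = Φ{[Φ⁻¹(p) − r·x] / √(1 − r²)}
- R² = Var[m(X)] / [p(1 − p)]
- SE ratio (adjusted to unadjusted risk difference) = √(1 − R²)
- equivalent N = 1750 / (1 − R²)
- power, from a base of 80% = Φ[(1.960 + 0.842)/√(1 − R²) − 1.960]

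Results across p = 20%, 35% and 50%:

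| r | R² | SE ratio | Equivalent N | 80% power becomes |
|---|---|---|---|---|
| 0.1 | 0.005–0.006 | 0.998–0.997 | 1759–1761 | 80.2% |
| 0.2 | 0.020–0.025 | 0.990–0.987 | 1785–1796 | 80.8–81.0% |
| 0.3 | 0.046–0.057 | 0.977–0.971 | 1833–1857 | 81.8–82.3% |
| 0.4 | 0.083–0.102 | 0.958–0.947 | 1908–1949 | 83.3–84.1% |
| 0.5 | 0.134–0.161 | 0.931–0.916 | 2020–2085 | 85.3–86.4% |

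Worked line, p = 35% and r = 0.5: R² = 0.155; √0.845 = 0.919; 1750/0.845 = 2071; 2.802/0.919 − 1.960 = 1.09, so power is 86.2%.

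**4. Does the gain survive the adjustment already planned?** The fair comparator is the stratification-adjusted analysis, not the unadjusted one. A simulation used 1750 babies, 1500 runs per value of r, prevalence about 35%, a true risk difference of about 6 points, a linear model with robust standard errors, and an assumed birthweight mix of 12%, 35% and 53%. Site was not modelled. Adding baseline temperature to a model already holding birthweight band gave:

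| r | SE, birthweight only | SE, plus temperature | Ratio |
|---|---|---|---|
| 0.1 | 0.02205 | 0.02199 | 0.997 |
| 0.2 | 0.02205 | 0.02180 | 0.988 |
| 0.3 | 0.02205 | 0.02147 | 0.974 |
| 0.4 | 0.02205 | 0.02101 | 0.953 |
| 0.5 | 0.02206 | 0.02040 | 0.925 |

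These agree with the analytic ratios, so under these assumptions birthweight adjustment does not absorb the gain.

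**The case against.** The strongest reply is that covariates for one secondary outcome belong in the statistical analysis plan. Section 10.2.2 defers to such a plan, leaves the hypothermia model open, and does not forbid further covariates. Unadjusted plus stratification-adjusted analysis is a conventional and valid pair. Part of this stands: a plan not seen here may already name baseline temperature, and nothing in the protocol is false or self-contradictory. But the section is not silent. It names an adjustment set and lays down a rule for additions, and that rule is the weak part. An analysis plan that follows it inherits the weakness; one that departs from it should have the protocol aligned.

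A reader might go further and infer that the trial is certain to lose worthwhile precision. The documents do not support that. Babies enter at 1 to 48 hours of age and both arms then receive thermal support, so the correlation may be as low as 0.1 to 0.2, where the gain is negligible. Nor do they support treating the pre-randomisation timing as settled: Section 3.2.1 makes allocation conditional on screening data, and the screening steps in Section 5.2 do not include temperature. The place of hypothermia at the top of the list in Section 1.4.2 also carries no stated rank.

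One technical reservation stands in full. For a binary outcome, adding a covariate does not shrink the standard error of a conditional odds ratio. The narrower interval applies to a standardised risk ratio or risk difference; on the odds-ratio scale the benefit appears as power.

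**Conclusion.** The point holds as a minor, nearly free improvement. The non-exploratory analyses stated for 24-hour hypothermia omit mean baseline axillary temperature, and the only stated way to include it is a data-driven check on imbalance that takes no account of prognostic value.

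The gain is unknown and lies between nil and modest: under the assumptions above, a standard error lower by about 0.3% to 8%, and 80% power becoming about 80% to 86%. This rests on an assumed correlation of 0.1 to 0.5, an assumed prevalence of 20% to 50%, a normal model for temperature, and temperature being taken before randomisation. The primary outcome, the sample size and the validity of the comparison are untouched.

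**What to change.** In Section 10.2.2, or in the analysis plan with the protocol aligned to it, before unblinding:

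- Name mean baseline axillary temperature (the average of the three readings) as a continuous covariate, together with birthweight band and site, in the adjusted analysis of hypothermia at 24 hours, whatever the observed balance.
- Report a standardised (marginal) risk ratio or risk difference from that model with its 95% confidence interval, and the unadjusted figure alongside.
- Confirm in Section 5.6 that baseline temperature counts among the data required before randomisation.

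The cost is a few lines of wording and no new data. It does commit the analysis to an effect measure that the protocol now leaves open for this outcome. A few missing baseline temperatures would need simple imputation so that no baby drops out of the adjusted analysis. If the correlation proves small, almost nothing is lost.

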5.6 Randomisation

Randomisation will take place following collection of necessary baseline data and before the intervention or control procedures start. The details of the randomisation method are outlined in section 3.2.1. In situations where both twins are eligible for enrollment, they will be allocated to the same arm.

5.7 Intervention and Control Arms

After the completion of recruitment and randomisation procedures and any required medical procedures according to clinical care guidelines, neonates will be allocated to receive either the intervention or standard care.

5.7.1 Delivering the intervention arm

KMC will be initiated as soon as possible following randomisation. Neonates allocated to the intervention arm will be naked except for hat and diaper. They will be secured to the exposed chest of the mother/caregiver using a KMC wrap. Prior to placing the neonate in the skin-to-skin position, a study nurse or medical officer will attach a pulse oximetry probe to the hand and a temperature probe to the torso. These procedures will take place in the admission area, prior to moving the baby to the study area. On arrival at the study area, the mother/caregiver will be seated on an adjustable bed. If required, oxygen will be provided from a cylinder or concentrator (depending on available resources at each site). Oxygen will be delivered to the neonate via nasal cannula or mask (if CPAP is required). If IV fluids are required, a bag of IV fluids will be hung and an IV cannula will be placed by a study nurse or medical officer. The study nurse or medical officer will then initiate IV fluids, with drip rate calculated according to standardised guidelines. If the mother/caregiver needs to take a short break (e.g., to shower or use the restroom), the neonate will be placed in an incubator or under a radiant heater. Every effort will be made to encourage skin-to-skin contact for 18h/day, unless otherwise clinically indicated. While we anticipate the mother will be the primary KMC provider, a family member or close friend (helper) may also provide skin-to-skin care in order to avoid disruptions. Clinical study staff at each site will counsel mothers/caregivers about KMC throughout the hospital stay, including the time of discharge. In addition, mothers who practised KMC as participants may be engaged as peer-counsellors when they return for follow-up. For each episode of skin-to-skin contact, the caregiver providing KMC (e.g., mother, father, helper) and the time of initiation and duration will be monitored and recorded in the electronic CRF (using bedside tablets).

5.7.2 Delivering the control arm

Neonates allocated to the control arm will be placed in an incubator or under a radiant heater, as per standard management at the study sites. They will wear a hat and be wrapped as per standard care. Oxygen will be provided from an oxygen cylinder or concentrator and IV fluids will be securely attached via an IV cannula with drip rate calculated, as in the intervention arm. The pulse oximeter will be placed inside the incubator or next to the radiant heater. The parent/caregiver will be able to touch the baby, if

requested, but will not provide any skin-to-skin contact until he/she meets clinical stability criteria (see Section 3.2.5), which are consistent with those used in the WHO I-KMC trial and in line with standard clinical procedures at the study sites. Once stable, the baby can transition to routine (intermittent) KMC with the parent/caregiver in a chair or bed in the study area.

5.8 Follow-up

Participants will be followed daily while admitted to the hospital (see section 6.1.2 for additional details).

At the time of discharge, all parents/caregivers will be provided with an illustrated handout on neonatal danger signs and instructed to contact the site study team or seek medical help if their baby becomes unwell. All families will be provided with phone numbers to contact the study team and a study participant ID card. Parents/caregivers will receive UgSh 20,000 (per enrolled neonate) to cover the costs of transport home and they will be able to keep the KMC wrap, so they can continue KMC at home (parents/caregivers of babies in both arms will be encouraged to continue KMC at home).

All participants will be given an appointment to attend the neonatal follow-up clinic at the respective study site on day 28-30. Transport costs (UgSh 20,000 per enrolled neonate) will also be provided to cover the costs of return transport to the study site for the follow-up visit. At this visit, repeat cUS (KNRH and JH only) and anthropometry will be performed; feeding practices and outcomes (alive, dead, readmitted) will be documented; and the WCI and Maternal Infant Responsiveness Instrument (MIRI) questionnaires will be administered to mothers.

If participants are discharged prior to day 7, additional follow-up will be arranged according to study site:

- At KNRH and JH, participants will be given an additional appointment to attend the neonatal follow-up clinic on day 7, where repeat cUS will be performed and outcomes (vital status, readmitted) will be recorded. If day 7 falls on a weekend, participants will be phoned on day 7 to ascertain outcome and the appointment will be made for the closest working day (e.g., if day 7 is Saturday, appointment on Friday; if day 7 is Sunday, appointment on Monday).
- At IH and MH, participants will be phoned on day 7 to ascertain outcome (alive, dead, readmitted) and reminded to attend the neonatal follow-up clinic appointment on day 28-30.

If participants do not attend follow-up clinic, a telephone call will be made the same day to ascertain outcome and feeding practices and to arrange follow-up, either in the clinic or at the families' home, as soon as possible. Routine follow-up beyond the planned study follow-ups will be provided by the study site staff according to standard practice and clinical need of the baby.

